9.2. Dosage and administration

The IMP (1 capsule b.i.d.) will be swallowed together with 200 mL of water in the morning and in the afternoon approximately 8 hours apart on each administration day, except for Day 56 and Day 84 when the dose will be taken in the morning at the clinic visit after trough PK sampling.

Dose run-in phase and treatment phase

Treatment allocation throughout the run-in and treatment dosing periods will be managed through the Interactive Response System (IRS) system. During the 9-day run-in phase, the IRS system will ensure all patients allocated to active dose regimen will receive 5 mg mesdopetam b.i.d, followed by the randomized dose at Visit 2 (Day 9). Patients allocated to placebo will receive placebo during the first week run-in and then continue placebo during the whole treatment period. Any dose reduction will also be managed through the IRS system to ensure that blinding is maintained.

If a patient experiences **increased parkinsonism** and/or **consistent increase in motor OFFtime**, during the treatment period from Visit 2 up to Visit 3 (i.e. Day $9 - Day 28 \pm 4 days$), the dosing can be reduced by 2.5 mg b.i.d. A dose reduction is allowed at only one occasion. A review of motor function will be performed at Visit 3.

The following tables give additional information on the two dose phases (Table 2) and the dose decrease guidance (Table 3).

Confidential	Version: 5.0	Page 39 of 74
Protocol: IRL790C005	Date: 5 Mar 2021	e

Table 2: Treatment period – dosing phases

Dose phase	Details
Dose run-in phase: Randomization Day 1. First dose taken Day 1 (evening dose) and last dose taken Day 9 (morning dose).	All patients randomized to mesdopetam will receive 5 mg b.i.d. All patients randomized to placebo will receive placebo b.i.d.
Dosing following Visit 2: First dose taken Day 9 (evening dose) and last dose taken Day 84 (morning dose/at the clinic due to PK sampling)	All patients randomized to mesdopetam will receive mesdopetam 2.5 mg, 5 mg or 7.5 mg b.i.d., as randomized. All patients randomized to placebo will continue with placebo b.i.d.

Table 3: Dose decrease guidance

Treatment period	Dose decrease guidance
Applicable for treatment from Visit 2 (Day 9) until Visit 3 (Day 28 ±4 days):	Decision to reduce the dosing is only allowed from Visit 2 (Day 9) until Visit 3 (Day 28 ± 4 days), and dose reduction is only allowed once.

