10.5. Visit 2 (Day 9 + 2 days)

The following procedures and assessments are to be carried out at Visit 2:

- Allocation of randomized dose of mesdopetam/placebo. Managed through IRS system.
- Dispense and collect empty bottle of IMP
- Concomitant Medications
- AEs/SAEs
- IMP compliance

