5 RANDOMIZATION

At the baseline visit (Visit 1, Day 1) patients will be randomized 1:1:1:1 to receive one of three doses of mesdopetam (2.5 mg, 5 mg, or 7.5 mg) or placebo b.i.d. based on the randomization schedule prepared by the unblinded statistician.

During the first week (Day 1 evening dose to Day 9 morning dose) a run-in phase with either 5 mg mesdopetam or placebo b.i.d. will take place, during which all patients allocated to mesdopetam will receive 5 mg mesdopetam b.i.d. and patients allocated to placebo will receive placebo b.i.d. The purpose of the run-in period with 5 mg b.i.d. is to allow for a one-week dose titration for patients randomized to 7.5 mg b.i.d. In a previous Phase 2a study most patients tolerated 5 mg b.i.d. At Visit 2 (Day 9), patients will receive mesdopetam 2.5 mg, 5 mg or 7.5 mg or placebo b.i.d., as randomized.

Randomization will be performed via a web-based Interactive Response System (IRS), using a dynamic balancing (minimization) algorithm. Randomization will be stratified by average (based on at least two valid home diaries) of <6 daily hours and \geq 6 hours of daily ON-time with troublesome dyskinesia at baseline.

During the one-week run-in phase, the IRS will ensure all patients allocated to mesdopetam treatment will receive 5 mg mesdopetam b.i.d., followed by the randomized dose during the treatment period. Patients allocated to placebo will receive placebo during the first week run-in and then continue placebo during the whole treatment period. Any dose reduction will also be managed through the IRS to ensure that blinding is maintained.

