6.10 Exposure to Study Drug

Exposure to study drug will be calculated as follows from the date of last dosing minus the first day of dosing + 1. The exposure calculation will not take into account breaks in therapy.

Exposure	Calculation
Exposure to 5 mg during run-in period (all patients)	Dispensing Date (Visit 2, Day 9) – Date of First Dose + 1
Exposure to randomized dose if the patient did not have a dose reduction	Date of Last Dose – Dispensing Date (Visit 2, Day 9) + 1
Exposure to randomized dose if the patient had a dose reduction	First dispensing date where dose is different to randomized dose – Dispensing Date (Visit 2, Day 9) + 1
Exposure to adjusted dose if the patient had a dose reduction	Date of Last Dose – First dispensing date where dose is different to randomized dose + 1
	(programming checks should be made to ensure the adjusted dose was also dispensed at Visit 3, Day 28)

Exposure to each dose level will be calculated as follows:

In the rare case that a kit was dispensed containing the wrong dose then those records will be excluded from calculations.

Extent of exposure (number of days of exposure to study drug) will be presented by each treatment group and combined based on the randomized treatment. A separate tabulation will also be provided to present the exposure during the run-in period and the period after receiving the randomized dose.

All reported data will also be listed.

QMD Ref: Worldwide-TMP-ST-005-7.0 Effective: 12Aug2019	Governing QMD: Worldwide-SOP-ST-001
Confidentiality	y Statement
This document is the property of Worldwide Clinical Trials Inc. and may no prior approval from Worldwide Quality Assurance or in compl	
REF: Worldwide-TMP-QA-001f-1.3	Page 26 of 49

Worldwide Clinical Trials Controlled Quality Management Document		
WORLDWIDE CLINICAL TRIALS	Sponsor:	Integrative Research Laboratories Sweden AB
	Protocol Number:	IRL790C005
STATISTICAL ANALYSIS PLAN. PHASE 2-3-4		

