6.17 Safety Analyses

Safety analyses will be presented by actual treatment group as well as adjusted dose group for all patients in the SAS.

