6.17.1 Adverse Events

Adverse events will be collected from the time of informed consent and continues through the last follow-up assessment in the study.

A treatment emergent adverse event (TEAE) is defined as:

- Any AE that has an onset on or after the first dose of study drug through the last follow-up assessment in the study.
- Any pre-existing AE that has worsened in severity on or after the first dose of study drug through the last follow-up assessment in the study.

A treatment-related AE is defined as an AE relationship to study drug classified by the Investigator as 'possible', or 'probable'. If an AE has missing relationship, 'probable' will be assumed for analysis purposes.

Severity of the AE will be graded using the Common Terminology Criteria for Adverse Events (CTCAE) grading system (Version 5.0): Grade 1 (Mild), Grade 2 (Moderate), Grade 3 (Severe), Grade 4 (Life-Threatening), Grade 5 (Fatal). Grade 3 (Severe) will be assumed for an AE with missing grade.

An overall summary table of AE incidence (number and percent of patients) and number of events, will be presented by treatment group and overall, for the following categories:

Any Reported TEAE

 QMD Ref: Worldwide-TMP-ST-005-7.0 Effective: 12Aug2019
 Governing QMD: Worldwide-SOP-ST-001

 Confidentiality Statement

 This document is the property of Worldwide Clinical Trials Inc. and may not be duplicated, copied, altered or removed from company without
 prior approval from Worldwide Quality Assurance or in compliance with Worldwide Standard Operating Procedures.

 REF: Worldwide-TMP-QA-001f-1.3
 Page 42 of 49

- **Treatment-Related TEAEs**
- Serious TEAEs
- Serious Treatment-Related TEAEs
- TEAEs Leading to Reduction in Dose of Study Drug
- TEAEs Leading to Interruption of Study Drug
- TEAEs Leading to Withdrawal of Study Drug
- TEAEs Leading to Early Withdrawal from Study •
- **TEAEs** Leading to Death •

Summaries of TEAE incidence and number of events by SOC and PT will be presented by treatment group and overall, for the following:

- TEAEs
- Treatment-related TEAEs •
- Serious TEAEs
- Serious Treatment-Related TEAEs
- TEAEs by Maximum Grade, (incidence only)
- Treatment-Related TEAEs by Maximum Grade, (incidence only)
- TEAEs by Strongest Relationship, (incidence only)
- Treatment-Related TEAEs by Strongest Relationship, (incidence only)

The following listings of AEs will be presented in Section 14.3.2 of the CSR:

- Serious AEs
- TEAEs Leading to Interruption of Study Drug

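### Adverse events starting in the 5 mg run-in are tabulated under each patient's actual or adjusted dose group and never shown separately, which chiefly distorts the 2.5 mg column

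*SAP*

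**What the plan says.** Dosing: in the run-in "all patients allocated to mesdopetam will receive 5 mg mesdopetam b.i.d. and patients allocated to placebo will receive placebo b.i.d" (SAP 5). Protocol 9.2, Table 2, fixes the run-in as "First dose taken Day 1 (evening dose) and last dose taken Day 9 (morning dose") and the next phase as "First dose taken Day 9 (evening dose) and last dose taken Day 84 (morning dose/at the clinic due to PK sampling"). Protocol 10.5 sets the window as "Visit 2 (Day 9 + 2 days"), so the run-in can last to Day 11. SAP 5 describes the run-in as a titration step for the 7.5 mg arm.

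Adverse events: SAP 6.17.1 defines a TEAE as "Any AE that has an onset on or after the first dose of study drug through the last follow-up assessment in the study", plus earlier events that worsen after that dose. SAP 6.17 adds "Safety analyses will be presented by actual treatment group as well as adjusted dose group". The columns in SAP 6.3.6 are 2.5, 5 and 7.5 mg, all mesdopetam, and placebo. SAP 6.3.4 counts a patient once per preferred term and system organ class, at the highest severity, over all patients in the treatment group.

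Places where the run-in is treated as its own period: for exposure, "A separate tabulation will also be provided to present the exposure during the run-in period" and the period after it (SAP 6.10), and early-withdrawal assessments are mapped to run-in or later (SAP 6.2.3). Adverse events get no such split. They are summarised by month 1, 2 and 3 only.

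**The concern.** A 5 mg event in the first week marks a patient assigned to 2.5 mg in the 2.5 mg column for the rest of the study. Under the once-per-patient rule, a later event with the same term at 2.5 mg adds nothing unless it is more severe or more closely related. A patient who stops before Visit 2 has taken only 5 mg, yet is shown under 2.5 or 7.5 mg if that was the assigned arm.

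Neither existing device repairs this. The adjusted dose group (SAP 6.2.16) moves the whole patient down one dose after a permitted reduction. It ignores the dose at onset, so a patient reduced from 5 to 2.5 mg carries run-in and other pre-reduction 5 mg events into the 2.5 mg column. In the monthly summaries, month 1 contains the whole run-in, and an event counted as ongoing in month 2 or 3 may have begun in it.

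Safety and tolerability and the dose response are both secondary objectives, and protocol 4.3 and 6.2 expect the dose-response work to inform safety as well as effectiveness. The 2.5 mg column is the one most likely to be read as tolerability at the lowest dose, and its patients begin at twice that dose.

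**Working it through.** The plan gives no figure for this point, so the share of dosing is counted from the schedule. The counts assume two doses on every full day, full adherence and no dose reduction.

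**Doses, Visit 2 on Day 9 (protocol Table 2)**
- Run-in: 1 (Day 1 evening) + 7 × 2 (Days 2-8) + 1 (Day 9 morning) = 16.
- Whole period: 1 + 82 × 2 (Days 2-83) + 1 (Day 84 morning) = 166. The SAP 6.11 formula for expected doses with a final morning dose agrees: (84 − 1 − 1) × 2 + 2 = 166.
- At assigned dose: 166 − 16 = 150.
- Days 1-28: 1 + 27 × 2 = 55, of which 55 − 16 = 39 are at assigned dose. The SAP does not define its months in days; Days 1-28 stand in for month 1.
- Visit 2 on Day 11: run-in = 1 + 9 × 2 + 1 = 20.

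**Share of doses and mean dose**

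| Window | Run-in share | Mean dose, 2.5 mg arm | Mean dose, 7.5 mg arm | Contrast (nominal 3-fold) |
|---|---|---|---|---|
| Whole period | 16/166 = 9.6% (20/166 = 12.0% if Day 11) | (16×5 + 150×2.5)/166 = 2.74 mg | (16×5 + 150×7.5)/166 = 7.26 mg | 2.65-fold |
| Days 1-28 | 16/55 = 29% (20/55 = 36% if Day 11) | (16×5 + 39×2.5)/55 = 3.2 mg | (16×5 + 39×7.5)/55 = 6.8 mg | 2.1-fold |

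The SAP 6.17.1 incidence tables cover the whole period and follow-up, so the first row applies to them. The second row applies at most to the month 1 summary. Mean dose describes exposure; it does not say how many events are misplaced.

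**Effect on event rates (illustration only)**

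Let q be the run-in incidence, equal in expectation in all active arms because they take the same dose, and p the incidence after Visit 2. If the two are independent, the planned table shows 1 − (1 − q)(1 − p). The documents give neither q nor p. Assume p = 5%, 10% and 20% at 2.5, 5 and 7.5 mg:

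| q | 2.5 mg | 5 mg | 7.5 mg | 7.5 minus 2.5 | Ratio 7.5 to 2.5 |
|---|---|---|---|---|---|
| split table | 5% | 10% | 20% | 15.0 points | 4.0 |
| 5% | 9.8% | 14.5% | 24.0% | 14.2 points | 2.46 |
| 10% | 14.5% | 19.0% | 28.0% | 13.5 points | 1.93 |
| 20% | 24.0% | 28.0% | 36.0% | 12.0 points | 1.50 |
| 30% | 33.5% | 37.0% | 44.0% | 10.5 points | 1.31 |

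The difference shrinks by the factor (1 − q) and keeps its sign. The ratio falls faster, but how fast depends on the assumed p. At q = 10%, 10/14.5 = 69% of the patients counted in the 2.5 mg column had a run-in event, against 10/28 = 36% in the 7.5 mg column. This is why the lowest dose is affected most.

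**The case against.** Four points on the other side carry weight.

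- **The 7.5 mg arm.** Its run-in is planned titration, so those events are part of that regimen and belong in its overall column. A reader might infer that the 2.5 and 7.5 mg columns are distorted alike; SAP 5 does not support that. What remains for 7.5 mg is mainly the patient who stops before ever taking it.
- **Early clustering.** A reader might point to Phase 2a, where 9 of 39 mesdopetam patients (23%) reported parkinsonism during titration only and 2 of 39 (5%) at steady state (protocol 4.6). That scheme raised the dose until intolerability appeared, so the figures do not carry over to a fixed 5 mg week. Protocol 6.3 says most patients tolerated 5 mg b.i.d. well. Clustering in this run-in is possible but not shown.
- **Partial cover.** All adverse events are listed, run-in exposure is tabulated, months 2 and 3 are shown separately, and SAP 6 allows extra tables in the study report. Scheduled post-baseline vital signs start at Visit 3 and laboratory tests and ECGs at Visit 4, so the problem is confined to adverse events. None of this yields a run-in incidence by treatment, or a 2.5 mg incidence free of run-in onsets.
- **Descriptive status.** Safety is not formally tested (protocol 14.10), so no error rate or power figure changes.

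The wording of the SAP also matters. It groups by actual and adjusted dose, not by randomised dose, and does not define actual. For a patient without a dosing error who reaches Visit 2, actual and randomised dose coincide. For one who stops in the run-in, actual could mean the assigned arm or, literally, 5 mg. The first reading shows a dose never taken; the second moves the patient out of the assigned arm and changes the denominators.

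**Conclusion.** The point holds, as a cheap improvement to the safety tables. Followed as written, the plan enters events that began on 5 mg in the 2.5 mg column. With actual treatment read as the assigned arm, it also shows patients who stopped in the run-in under a dose they never took. No planned adverse event table lets the reader undo this.

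The size in dosing terms is 9.6% of scheduled doses over the treatment period (2.65-fold contrast between the 7.5 and 2.5 mg arms) and 29% within Days 1-28 (2.1-fold). A reader might take the 28-day figures as the size for the whole study; the incidence tables span the full period, so they are not. The size in event rates is unknown, because it depends on a run-in incidence that the documents do not give.

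A reader might also infer that the dose gradient could vanish or reverse. With the same run-in dose in every active arm, and run-in and later events taken as independent, the expected absolute gradient shrinks by (1 − q) and does not change sign.

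**What to change.** Keep the overall TEAE tables in SAP 6.17.1 and add tables by period of onset:

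- (a) Run-in: all mesdopetam (5 mg) versus placebo.
- (b) Onset from the first dose after Visit 2: by randomised dose and by adjusted dose group, with patients who entered that period as the denominator.

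State in which period an event starting on the Visit 2 date is counted. Protocol 12.8 collects a start time only for events on the day of first dosing, so the date alone cannot settle it, and the SAP 6.10 exposure formulas count the Visit 2 date in both periods. Define actual treatment group for a patient who stops before Visit 2.

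The cost is a few descriptive tables from onset and dispensing dates already collected. The downside is that table (b) leaves out patients who stopped in the run-in. It is therefore not a comparison of groups as randomised, and should be labelled so. Its adjusted-dose version will still move events between Visit 2 and a reduction along with the patient, which a footnote should say.

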	A dose reduction is only allowed if the patient experiences an increase in parkinsonism and/or a consistent increase in motor OFF-time. Increased parkinsonism is manifested as consistent increase in disability associated with parkinsonian symptoms (i.e. bradykinesia, tremor and/or rigidity).
	The following steps are permitted if the dose is decided to be reduced:
	Patients allocated to 7.5 mg b.i.d. \rightarrow dose is reduced to 5 mg b.i.d.
	Patients allocated to 5 mg b.i.d. \rightarrow dose is reduced to 2.5 mg b.i.d.
	Patients allocated to 2.5 mg b.i.d. \rightarrow dose is maintained (i.e. 2.5 mg b.i.d.).
	Patients allocated to placebo b.i.d. \rightarrow placebo b.i.d. is maintained.

Confidential	Version: 5.0	Page 40 of 74
Protocol: IRL790C005	Date: 5 Mar 2021	C

	If parkinsonism is still increased following this dose reduction, the patient and Investigator need to decide if the patient could continue with the same dose in the study (since the dose cannot be reduced further) or if the patient have to withdraw the IMP and the study. Dose reduction will be managed through the IRS system.
Patient motor function review performed at Visit 3 (Day 28 ±4 days)	This review is based on the 24-hour patient home diaries completed in the week prior to Visit 3 and the MDS-UPDRS part II assessment completed during site Visit 3. Diaries and MDS-UPDRS data are reviewed and compared to baseline.
	If there is a clinically relevant increase in OFF-time, the Investigator must determine if the increase has been consistent over time and if it is predominantly related to non-motor or motor OFF-time (according to the Investigator's clinical judgement). Evaluation of results from MDS-UPDRS part 2 (M-EDL) should be weighted in the decision. Adherence to prescribed antiparkinsonian medications should also be reviewed.
	Should a consistent increase in motor OFF-time, and/or a clinically significant worsening of mobility due to parkinsonism be assessed as likely due to the IMP, the dosing should be reduced by 2.5 mg b.i.d. at this visit. If the patient has already had a dose reduction prior to Visit 3, the dose cannot be reduced further at this visit, and the Investigator must determine whether the patient can continue in the study (i.e. continue in the study with the same dose).
	Other AEs not relating to the core symptoms of parkinsonism (such as, fatigue, headache, dystonia and other) do not qualify for dose reduction.

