12.3. Expectedness

An expected adverse reaction is an adverse reaction, the nature or severity of which is consistent with the applicable product information (Investigator's Brochure [8]), otherwise it is considered unexpected.

Based on non-clinical safety data in experimental animals as well as on Phase 1 data in healthy male volunteers and in patients with advanced PD (Phase 2a), AEs are likely to predominantly be CNS related. Adverse reactions in patients with advanced PD are listed below:

Table 4: Potential AEs associated with mesdopetam treatment	

Nervous system	Cardiac	General disorders and administration site condition	Musculoskeletal and connective tissue disorders
Parkinsonism	Postural dizziness	Lethargy	Muscular weakness
Tremor	Dyspnoea	Fatigue	
Muscular rigidity		Oedema	
Insomnia			
Somnolence			
Headache			
Slurred thinking			
Dissociation			
Balance disorder			
Dizziness			
			I
Confidential		Version: 5.0	

Confidential	Version: 5.0	Page 56 of 74
Protocol: IRL790C005	Date: 5 Mar 2021	6

Nervous system	Cardiac	General disorders and administration site condition	Musculoskeletal and connective tissue disorders
Concentration difficulties			
Gait freezing			
Fall			

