12.8. Recording adverse events

AEs identified using any of the following methods will be recorded:

AEs spontaneously reported by the patient

AEs observed by the Investigator or medical personnel

AEs elicited based on non-leading questions from the Investigator or medical personnel

Collection of AEs starts after the patient signs the ICF and continues until the last follow-up assessment. Any AE with start date on the day of first IMP administration must be recorded with start time.

At the follow-up visit, information on new AEs or SAEs, if any, and stop dates for AEs recorded and on-going during the dosing period must be recorded. AEs must be followed up until resolution or the follow-up assessment, whichever comes first.

AEs must be recorded on an AE Form in the CRF. The Investigator must provide information on the AE, preferably with a diagnosis or at least with signs and symptoms; start and stop

Confidential	Version: 5.0	Page 58 of 74
Protocol: IRL790C005	Date: 5 Mar 2021	5

dates, start and stop times (only applicable for AEs with start date on the day of first IMP administration); intensity; causal relationship to IMP; action taken, and outcome.

If the AE is serious, this must be indicated on the AE Form in the CRF. Furthermore, the Investigator must fill out the SAE Report Form and report the SAE to Worldwide Clinical Trials as described in Section 12.9.

AEs, including out-of-range clinically significant safety laboratory values, must be recorded individually, except when considered manifestations of the same medical condition or disease state; in such cases, they must be recorded under a single diagnosis.

If the severity/intensity of an AE increases a new AE Form must be completed in the CRF.

Patients with AEs occurring during the study must be treated according to clinical practice at the discretion of the Investigator.

It is the responsibility of the Investigator to follow up on all SAEs until the patient has recovered, stabilized, or recovered with sequelae and to report to the Sponsor all relevant new information using the same procedures and timelines as those for the initial report. Relevant information includes discharge summaries, autopsy reports, and medical consultation.

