6.1.3 Per Protocol Set

The Per Protocol Set (PPS) will consist of patients from the FAS without protocol deviations that impact the efficacy assessment. Situations which impact the efficacy assessment may include (but are not limited to) those patients who:

- Did not satisfy all of the inclusion/exclusion criteria
- Any patients with treatment administration errors
- Any patients taking inadmissible concomitant medications

Patients who are to be included or excluded from the PPS will be identified and listed following a Blind Data Review (BDR) performed prior to the conclusion of the clinical investigation, database lock and unblinding. Any deviation considered to have a serious impact on the efficacy results will lead to the relevant patient being excluded from the PPS. Any patient exclusions from PPS will be documented in a patient evaluability document before database lock.

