6.2.16 Definition of Adjusted Dose Group

To account for patients who have a permitted dose reduction and remain stable thereafter, adjusted dose groups will be defined. Patients randomly allocated to mesdopetam and who had a permitted dose reduction of 2.5 mg recorded at Visit 3, will be counted in the treatment group one dose lower than their randomized treatment. Patients randomly allocated to placebo but who had a dose reduction will remain in the placebo group.

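### No adverse event table described in the SAP gives the dose being taken at onset, so in the adjusted-dose display parkinsonism that led to a dose reduction is counted at the lower dose, and run-in events on 5 mg are counted under other doses

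*SAP*

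**What the plan says.** - **Tables.** SAP 6.17.1 plans patient-level summaries: "Summaries of TEAE incidence and number of events by SOC and PT will be presented by treatment group and overall". It adds an overall category table, with a row for events leading to dose reduction, and summaries by month. SAP 6.3.4 counts a patient once within each preferred term (PT) and each system organ class.
- **Grouping.** SAP 6.17: "Safety analyses will be presented by actual treatment group as well as adjusted dose group for all patients in the SAS".
- **Adjusted dose group.** Under SAP 6.2.16, a mesdopetam patient with a permitted reduction recorded at Visit 3 "will be counted in the treatment group one dose lower than their randomized treatment". Reduced placebo patients stay in placebo.
- **Run-in.** SAP 5 says that until the Day 9 morning dose "all patients allocated to mesdopetam will receive 5 mg mesdopetam b.i.d", whichever dose they were randomised to.
- **Grounds for reduction.** Protocol 9.2, Table 3 allows a reduction only between Visit 2 and Visit 3, and only for increased parkinsonism or a consistent rise in motor OFF-time. A patient on 2.5 mg stays on 2.5 mg.
- **Exposure.** SAP 6.10 already derives days on the 5 mg run-in, on the randomised dose and on the reduced dose. No corresponding split is described for adverse events.

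**The concern.** Increased parkinsonism was the most commonly reported adverse event on mesdopetam in Phase IIa. Protocol 4.3 cites it in explaining why this trial tests doses below 10 mg b.i.d. How often it occurs at each dose therefore bears directly on dose choice.

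The two planned displays classify patients, not events, by dose. Two misattributions follow.

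1. **Reduction.** A patient on 7.5 mg who develops parkinsonism and is stepped down to 5 mg has that event counted at 5 mg in the adjusted-dose display. The shift is directional, because the event being tabulated is itself a ground for moving the patient. Through reductions the 7.5 mg group can only lose patients and the 2.5 mg group can only gain them.
2. **Run-in.** An event in the first nine days of the 2.5 mg or 7.5 mg arm began on 5 mg. The actual-treatment display counts it under the arm's dose. The adjusted-dose display does the same for patients who were not reduced. A patient later reduced from 7.5 mg to 5 mg lands on the right dose there by coincidence, whereas one reduced from 5 mg to 2.5 mg does not.

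A dose-by-dose reading of parkinsonism could thus look flatter or steeper than it was, or even reversed.

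**Working it through.** **Share of dosing in the run-in.** From Protocol 9.2, Table 2:
- Run-in: Day 1 evening (1) + Days 2 to 8 at 2 a day (14) + Day 9 morning (1) = 16 doses.
- All treatment: Day 1 evening (1) + Days 2 to 83 at 2 a day (82 × 2 = 164) + Day 84 morning (1) = 166 doses.
- The compliance formula in SAP 6.11 for a last morning dose agrees: (84 − 1 − 1) × 2 + 2 = 166.
- Share: 16/166 = 9.6%.

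**Timing in Phase IIa.** Protocol 4.6 reports 9 mesdopetam patients with parkinsonism in titration only and 2 at steady state: 9/(9 + 2) = 81.8% early. Titration there was upward over two weeks until signs of intolerability, so this shows only that early onset is plausible. It is not a forecast for a fixed 5 mg run-in.

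**Effect of reassignment.** Arm size: 154/4 = 38.5, taken as 38. Event counts and step-downs are assumed, as the documents give none for this trial. If *r* affected patients step down from an arm with *x* affected of *N*, that group becomes (*x* − *r*)/(*N* − *r*) and the group below becomes (*x* + *r*)/(*N* + *r*).

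| Assumption (6/38 = 15.8% in each arm by actual treatment) | 7.5 mg | 5 mg | 2.5 mg |
|---|---|---|---|
| No reductions | 6/38 = 15.8% | 6/38 = 15.8% | 6/38 = 15.8% |
| 2 affected step down from 7.5 mg, none from 5 mg | 4/36 = 11.1% | 8/40 = 20.0% | 6/38 = 15.8% |
| 2 affected step down from each of 7.5 mg and 5 mg | 4/36 = 11.1% | (6 − 2 + 2)/38 = 15.8% | 8/40 = 20.0% |

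In the second row, a true difference of zero between 7.5 mg and 5 mg becomes 11.1 − 20.0 = −8.9 percentage points. In the third, a flat relation appears inverted. The first row is the case with no effect.

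**Counting across related terms (secondary).** Patients with at least one of several PTs number between the largest row and the sum of the rows, capped at *N*. Assume a Parkinsonism row of 6 of 38 and component rows for tremor, rigidity and bradykinesia:
- components total 0: 6 patients (15.8%);
- components total 2: 6 to 8 (15.8% to 8/38 = 21.1%);
- components total 7, none above 6: 6 to 13 (15.8% to 13/38 = 34.2%).

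**The case against.** The case against is substantial.

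- **The actual-treatment display is also required.** In the examples above it shows 6/38 in each arm, so a reader with both tables would see that the adjusted-dose pattern comes from reassignment. This stands and limits the first effect. It does nothing for run-in events.
- **Other outputs help.** A PT seen in more than 5% of participants is summarised by month. On 154 randomised, 5% is 7.7, so 8 patients. Action taken, including dose reduction, is recorded for each event, and all events are listed. The severity rating for overall Parkinson's disease has a patient-level shift table by dose and visit. Yet month 1 mixes run-in, randomised and reduced doses, listings leave the reconstruction to the reader, and the shift table does not count events.
- **The SAP allows further tables in the study report if warranted.** True, but a classification fixed before unblinding is worth more than one chosen afterwards.

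A reader might infer something stronger: that no output counts patients per dose with worsened parkinsonism. The documents do not support that. Each PT row is a patient count per dose, so a Parkinsonism row answers the question for that term. Protocol 12.3, Table 4 does list parkinsonism, tremor and muscular rigidity separately, and no grouped term is defined. However, Protocol 12.8 says of manifestations of the same condition that "in such cases, they must be recorded under a single diagnosis", and Phase IIa cases were reported as parkinsonism. The loss from having no grouped row may be zero.

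**Conclusion.** The point holds as a modest improvement to consider, not as an error in the plan. No adverse event table described in the SAP gives dose at onset. The adjusted-dose display can credit parkinsonism to the dose reached after the reduction it caused, and neither display systematically assigns run-in events to 5 mg.

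The size cannot be known from the documents. It depends on how many affected patients are reduced and how many events start in the first nine days. The 11.1% against 20.0% contrast rests on assumed counts. Protocol 6.3 says 5 mg b.i.d. was well tolerated by the great majority of patients, so run-in events may be few. I read actual treatment group as the arm whose medication the patient received, since SAP 6.17 does not define it further. The table shells were not available, so the statement covers only what the SAP text describes.

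It would go too far to say that the plan hides a safety signal. The actual-treatment display preserves the randomised comparison.

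**What to change.** Before unblinding, add to SAP 6.17.1 one table of TEAEs by dose at onset, at least for parkinsonism: 5 mg run-in, randomised dose after Visit 2 (by dose), reduced dose (by dose), and placebo. State the rules:

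- An event starting before a reduction belongs to the dose then being taken.
- An event starting on the day of a switch belongs to the earlier dose. A rule is needed because Protocol 12.8 collects start times only on the first dosing day.
- A patient may appear in more than one dose period, so columns need not sum to arm totals.

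Show exposure time beside the counts, using the SAP 6.10 derivations. Time at risk differs between periods, and patients on a reduced dose are selected by their course, so comparisons across periods are descriptive only.

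Optionally, add one row counting each patient once across parkinsonism-related PTs, next to the Parkinsonism PT row. Fix its term list at the planned "Blind Data Review (BDR) performed prior to the conclusion of the clinical investigation, database lock and unblinding". The row may add nothing, and it may pick up isolated tremor that does not meet the protocol's description of increased parkinsonism, so it should not replace the narrow row.

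The cost is one descriptive table programmed from onset and dispensing dates already collected.
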